4.7.3. Other safety endpoints

4.7.3. 1. Laboratory data

Quantitative descriptions of laboratory data will be performed on normalized values as outlined in Section 3.3 with the exception of hematology differential counts for which standardized values will be used because values collected as a ratio of WBC count cannot be normalized into a range in absolute unit. For these parameters results expressed in percentages of WBC will be converted to absolute count by multiplying WBC count by the value collected in percentage (ranges will not be transformed).

4.7.3. 1.1. Patient level analyses

All laboratory values will be reported in SI units. Summary displays for laboratory safety data (hematology and chemistry) will be produced by visit for both observed and change from baseline values of the different laboratory analyses. Laboratory tests taken only at screening, those in case of a qualifying event (e.g., thrombosis or hemolysis), and urine protein reagent strip test results will be presented in the laboratory listings. The following clinical parameters will be summarized:

- Hematology:
 - Complete blood count + differentials, hemoglobin (Hb), mean corpuscular volume (MCV), platelet counts
 - Haptoglobin
- Biochemistry:
 - Creatinemia, glomerular filtration rate according to MDRD
 - LDH
 - Total and free bilirubin (total bilirubin in all patients; if total bilirubin > ULN, free bilirubin will be assessed from the same blood sample, as total bilirubin)
 - AST, ALT, alkaline phosphatase (ALP), γ GT
 - Total serum protein level
 - Serum IgA levels

Laboratory values will be classified as normal, low, or high based on standardized normal ranges. Laboratory categories will be expressed in terms of the L (below lower limit of normal [LLN]), N (between LLN and ULN) and H (above ULN) classifications for numerical measurements and normal, abnormal for categorical measurements. The number and percentage of patients with abnormal values will be summarized for each laboratory parameter by visit. These summaries will include the number and percentage of patients with “any pre-treatment visit” and “any on-treatment visit post baseline” abnormality for each parameter. These displays will ensure that all abnormal values will be captured.

LNH shifts in clinical laboratory values (hematology and chemistry) from baseline to each visit post first dosing will be summarized by visit. Patients with values outside the normal range will be flagged.

A scatter plot of the values at the EOS assessment as well as the minimum and maximum values of each patient during the treatment follow-up against the values at baseline will be prepared for each parameter. The first diagonal will be displayed by a dotted line.

4.7.3. 1.2. Course and infusion level analyses

Descriptive statistics of laboratory parameters at screening, before and 96h after the 1st IMP course, before the start of each subsequent course and at the EOS assessment will be provided for laboratory parameters as well as for the clinical assessment. The change from before first IMP course to 96h after the 1st IMP course as well as to before subsequent courses will be presented as well as the minimum and maximum values of each patient during the complete treatment follow-up. The complete treatment follow-up of maximum and minimum presentations includes all post-baseline assessments, along with any unscheduled assessment results which do not contribute to by visit descriptive summaries. Similarly, shift tables for the clinical assessment will be produced showing the change from before the first IMP course to 96h after the 1st IMP course as well as to before subsequent courses.

A graphical display of the evolution of each laboratory parameter by course will be presented with connected box-and-whisker plots. The number of observations at each visit will be displayed in the graph.

Detection of hemolysis will be evaluated at course level. The number and percentage of course with hemolysis will be displayed by subgroup and overall in accordance with the IVIg-associated hemolysis criteria published by Health Canada ([Health Canada 2009](#)), adapted to the study as follows:

- Drop in hemoglobin by at least 1 g/dL compared to baseline and
- At least one of the two criteria below are met
 - Positive direct Coombs test
 - At least 2 of the following criteria are met (in absence of negative direct Coombs test):
 - * Reticulocyte count increased by at least $50 \times 10^9/L$ compared to baseline
 - * LDH increased by at least 20% compared to baseline
 - * Haptoglobin value is lower than the lower limit of normal (LLN)
 - * Free bilirubin (or total bilirubin if the free bilirubin is not documented) increased compared to baseline and value is greater than the upper limit of normal (ULN)

In the following situations the courses will be excluded from the analysis:

Criterion for hemoglobin value cannot be evaluated/calculated

Criterion for hemoglobin is evaluable, direct Coombs test neither positive or negative (missing or not-done) and

- 3 or 4 out of 4 criteria (Reticulocytes, LDH, Haptoglobin, free/total bilirubin) cannot be evaluated/calculated or
- 1 or 2 out of 4 criteria (Reticulocytes, LDH, Haptoglobin, free/total bilirubin) cannot be evaluated/calculated and less than two of the remaining criteria are met

A listing of all hemoglobin, reticulocytes, LDH, haptoglobin and bilirubin values will be provided for patients with at least one blood sample for which the aforementioned criteria for hemolysis is met. A listing of the excluded courses will be also given.

All abnormalities, clinically significant or not, will be listed. Pregnancy status and test results will also be listed, including the method of contraception used (if any).

4.7.3. 2. *Vital signs*

Vital signs parameters including systolic and diastolic blood pressure (mmHg), heart rate (bpm), weight, and body temperature (°C) (calculated value according to the way the temperature was measured) will be summarized.

4.7.3. 2.1. Patient level analyses

Descriptive statistics of vital sign values will be presented for the following time points:

- a) Screening
- b) Before the 1st IMP infusion
- c) 30-45 min and 60-75 min after the start of the first infusion
- d) 30-45 min after the end of the first infusion
- e) 96h after the end of the 1st course
- f) EOS

Change from time point b) will be presented for time points c) to e). The minimum and maximum of each parameter during the patient's complete treatment follow-up will be presented. The complete treatment follow-up of maximum and minimum presentations includes all post-baseline assessments, along with unscheduled assessment results which do not contribute to by visit and by timepoint descriptive summaries.

A scatter plot of the values at the end of study assessment as well as the minimum and maximum values of each patient during the treatment follow-up against the values at baseline will be prepared for each parameter. The first diagonal will be displayed by a dotted line.

4.7.3. 2.2. Course and infusion level analyses

Descriptive statistics of vital sign values will be presented at the following time points:

- a) Before the start of the course (only first infusion of a course)
- b) 30-45 min and 60-75 min after the start of the infusion
- c) 30-45 min after the end of the infusion

Change from before start of the course to time points b) and c) will be presented as well.

A graphical display of the evolution pre-dose values (before IMP infusion) of each vital sign parameter over time (by course). The evolution of (before start of the course, time points b) and c) at each day) will be also presented with connected box-and-whisker plots by course. The number of observations at each visit will be displayed in all graphs.

All abnormalities, clinically significant or not, will be listed in both patient level and course/infusion level formats. If a patient assessment has no timepoint attributed then these assessments are classified as unscheduled.

4.7.3. 3. *Thrombo-embolic physical examination*

Number and percentage of patients with at least one abnormal thrombo-embolic sign will be presented by visit together with the absolute number of signs for the following:

- Arterial thrombo-embolic signs
- Venous thrombo-embolic signs

4.7.3. 4. *Complete physical examination*

Physical examination results will be listed.

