3.3. Handling of Local Laboratory Data

Local laboratory data will first be standardized. Standardization is the process of converting original local laboratory results to agreed standard international (SI) units. This process allows laboratory parameters to be presented in the same measurement units across the study.

Given that local laboratories are utilized for the study, normalization of the laboratory results will be performed ([Karvanen 2003](#)). Normalization is the process of transforming results from different local laboratories in such a way that the results are directly comparable. For normalization the parameter lower and upper limits from a local laboratory (S_{Lo}, S_{Up} - see Section [5.7.6. 1](#)) provided by Clinical Research Physician are chosen to represent a standard laboratory. The standardized reported result (R_S) and the local lower and upper limits for given parameter (I_{Lo}, I_{Up}) are then placed into an expression, of which the now normalized result (R_N) may be treated as if it was obtained from a central laboratory.

$$\text{Either } R_N = S_{Lo} + \left(\frac{R_N - I_{Lo}}{I_{Up} - I_{Lo}} \right) \times (S_{Up} - S_{Lo}) \text{ known as location-scale formula}$$
$$\text{Or } R_N = R_S \times \left(\frac{I_{Lo}}{S_{Lo}} \right) \text{ known as the scale formula}$$

Note that standardization (i.e., unit conversion to SI unit) will be done prior to normalization; this allows the laboratory results to be converted to the same measurements prior to being transformed so that results can be directly comparable.

The normalized result will be used for descriptive summaries; displays of laboratory categories such as abnormalities and shifts from baseline based on Low (below lower limit of normal [LLN]), Normal (between LLN and upper limit of normal [ULN]) and High (above ULN) classifications and displays for observed and change values. When normalization of a parameter is not possible (e.g. estimated Glomerular Filtration Rate), then the untransformed standardized result will be presented.

Normalizations will be performed using the ranges provided in Section [5.7.6. 1](#).

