5.7.6. Reference tables for derivations

5.7.6. 1. Reference ranges for local laboratory normalization

The following ranges have been reviewed and agreed by LFB Clinical Research Physician of the study:

Table 5–1: Reference ranges for normalization of local laboratory data

Laboratory test			Reference Ranges		Formula
Test name	Short name	Standard Units	Lower Limit of Normal (LLN): S_{Lo}	Upper Limit of Normal (ULN): S_{Up}	
Alanine Aminotransferase	ALT	IU/L	5	35	location-scale
Alkaline Phosphatase	ALP	IU/L	42	141	location-scale
Aspartate Aminotransferase	AST	IU/L	8	30	location-scale
Bilirubin	BILI	$\mu\text{mol/L}$	3	17	location-scale
Bilirubin, Free	BILIF	mg/dL	0,2	0,8	location-scale
Creatinine	CREAT	$\mu\text{mol/L}$	44	106	location-scale
D-Dimer	DDIMER	ug/L	0	500	location-scale
Ery. Mean Corpuscular Volume	MCV	fL	79	96	location-scale
Erythrocytes	RBC	$10^{12}/\text{L}$	4	5	location-scale
Gamma Glutamyl Transferase	GGT	IU/L	8	35	location-scale
Glomerular Filtration Rate	GFR	$\text{mL}/\text{min}/1.73\text{m}^2$	60	.	scale
Haptoglobin	HAPTOG	mg/dL	40	200	location-scale
Hematocrit	HCT	%	36	48	location-scale
Hemoglobin	HGB	g/dL	12	16	location-scale
Hemoglobin A1C	HBA1C	mmol/mol	20	42	location-scale
Lactate Dehydrogenase	LDH	IU/L	250	450	location-scale
Leukocytes	WBC	$10^9/\text{L}$	4	10	location-scale
Platelets	PLAT	$10^9/\text{L}$	150	450	location-scale
Protein	PROT	g/dL	6	8	location-scale
Protein Excretion Rate	PROTEXR	mg/day	0	100	location-scale

5.7.6. 2. Normative values for grip strength

Normative values ([Merkies 2000](#)) for quantitative grip strength assessment with the Martin vigorimeter for both hands in healthy subjects (kPa) are presented in [Table 5–2](#):

Table 5–2: Normative values for grip strength

Age (year)	Median values (KPa) per age span and gender	
	Males	Females
15-19	122	90
20-24	146	106
25-29	154	112
30-34	153	109
35-39	148	104
40-44	141	104
45-49	134	98
50-54	126	92
55-59	116	84
60-64	105	76
65-69	97	71
70-74	91	67
75-79	82	63
80-84	75	59
≥85	64	54

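### Differentials reported in percent are converted to absolute counts while their ranges stay in percent, and the SAP gives no matching-unit rule for low/normal/high flags and shift tables

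*SAP*

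**What the plan says.** SAP 4.7.3.1 sets a general rule and one exception: "Quantitative descriptions of laboratory data will be performed on normalized values as outlined in Section 3.3 with the exception of hematology differential counts". The reason given is that "values collected as a ratio of WBC count cannot be normalized into a range in absolute unit". Differential results that arrive as percentages are therefore "converted to absolute count by multiplying WBC count by the value collected in percentage (ranges will not be transformed").

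SAP 4.7.3.1.1 lists the haematology parameters to be summarised, including "Complete blood count + differentials, hemoglobin (Hb), mean corpuscular volume (MCV), platelet counts". It then states: "Laboratory values will be classified as normal, low, or high based on standardized normal ranges". It calls for abnormality counts by visit for each parameter and for low/normal/high shift tables from baseline for haematology and chemistry. It contains no separate rule for differentials.

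SAP 3.3 ties the summaries and the categories to the same value: "The normalized result will be used for descriptive summaries; displays of laboratory categories such as abnormalities and shifts from baseline". Where a parameter cannot be normalised, "then the untransformed standardized result will be presented". The range to be used for classification in that case is not named.

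Table 5-1 in SAP 5.7.6 ("Reference ranges for normalization of local laboratory data") gives leukocytes as 4 to 10 × 10⁹/L and has no row for neutrophils, lymphocytes, monocytes, eosinophils or basophils.

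**The concern.** For a differential reported in percent, the result changes unit and the local range expressly does not. The plan then asks for a low/normal/high flag and supplies no absolute range. A programmer who follows the SAP as written holds a count in 10⁹/L, a range in percent and an instruction to classify one against the other.

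At stake is the usefulness of the flag-based displays for these results. The SAP gives the abnormality tables the purpose of capturing every abnormal value. If almost all neutrophil values at a percent-reporting laboratory are Low at baseline and afterwards, the shift table shows Low to Low throughout and cannot show a real fall. The blood count with differentials is scheduled at 10 of 11 visits (SAP 2.6), and results come from local laboratories at approximately 37 sites (Protocol 3.3) or 42 (Protocol synopsis). Results in mixed units are therefore plausible, and SAP 4.7.3.1 itself provides for them.

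**Working it through.** The plan states no figure on this point, so there is nothing to reproduce. The check is one of units.

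**Inputs.** WBC 4 to 10 × 10⁹/L is the leukocyte range in Table 5-1. The documents give no local percent ranges. Those used here are assumptions for illustration: neutrophils 40–75, lymphocytes 20–45, monocytes 2–10, eosinophils 0–6 or 1–6, basophils 0–1.

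**Formula.** Converted count = WBC × percent / 100. The literal reading compares this count with the percent limits. The matched reading compares the original percent with the percent limits.

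**Single values at WBC 6.0**

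| Cell type | Percent | Converted count | Assumed range (%) | Literal flag | Matched flag |
|---|---|---|---|---|---|
| Neutrophils | 60 | 6.0 × 60/100 = 3.6 | 40–75 | Low | Normal |
| Lymphocytes | 30 | 6.0 × 30/100 = 1.8 | 20–45 | Low | Normal |
| Eosinophils | 15 | 6.0 × 15/100 = 0.9 | 0–6 | Normal | High |
| Eosinophils | 15 | 6.0 × 15/100 = 0.9 | 1–6 | Low | High |
| Basophils | 0.5 | 6.0 × 0.5/100 = 0.03 | 0–1 | Normal | Normal |

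**Whole in-range region.** The largest converted count from an in-range percentage occurs at WBC 10 and the upper percent limit:

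- Neutrophils: 10 × 75/100 = 7.5, below 40.
- Lymphocytes: 10 × 45/100 = 4.5, below 20.
- Monocytes: 10 × 10/100 = 1.0, below 2.
- Eosinophils (range 1–6): 10 × 6/100 = 0.6, below 1.

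For these four, 100% of in-range values at WBC 4–10 are flagged Low. A grid over WBC and percent gave the same result. With a lower limit of 0 (basophils, eosinophils 0–6), no value can be Low and all in-range values stay Normal. The error there is in the other direction: at WBC 6.0, a High eosinophil flag would need 6.0 × p/100 > 6, that is p above 100%, which cannot occur.

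**Effect on a shift.** Suppose a patient goes from WBC 6.0 with neutrophils 60% to WBC 4.0 with neutrophils 20%. The counts are 3.6 and 4.0 × 20/100 = 0.8. The literal flags are Low to Low. The matched flags are Normal (60 within 40–75) to Low (20 below 40).

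**Dependence on coding.** If the range is stored as a fraction (0.40–0.75), 3.6 is flagged High instead. The direction of the error depends on cell type and storage. The mismatch does not.

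**After the fix.** With result and range in the same unit, all in-range values on the grid are Normal for every cell type.

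**The case against.** The strongest reply is that the SAP never says the converted count is flagged against the percent range. The conversion sits in a paragraph about quantitative descriptions, and classification comes later in its own subsection. Leaving the ranges alone would be harmless if flags were taken from the original percent and its own percent range. A reader might infer that the plan does flag normal values as Low; the documents do not go that far. What remains is that the harmless reading is written nowhere. It also fits poorly with SAP 3.3, which uses one value for summaries and categories, and with classification on standardised ranges, which do not exist for these results.

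A reader might also infer that real cytopenias would go unseen. That is not supported. Absolute counts and changes are summarised by visit, with minima, maxima and plots (SAP 4.7.3.1.1 and 4.7.3.1.2). All data are listed (SAP 5.1), with listings showing the values as recorded (SAP 3.2). Laboratory findings that the investigator judges clinically significant are adverse events (Protocol 9.5.1).

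The absence of an explicit division by 100 is at most a matter of wording. Taking 60% as 0.60 gives 3.6. The product 6.0 × 60 = 360 needs an unnatural reading.

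Finally, near-universal Low flags would probably be noticed in the statistical review planned in SAP 5.5. That lowers the practical risk. It does not supply the missing rule, and missed highs would be much less conspicuous.

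**Conclusion.** The point holds as a defect in the stated rules: for percent-reported differentials, applying SAP 3.3, 4.7.3.1 and 4.7.3.1.1 as written pairs a value and a range in different units, and Table 5-1 offers no alternative range. Under the assumed percent ranges and WBC 4–10, all in-range neutrophil and lymphocyte values would be flagged Low, and true highs would be missed for cell types whose lower limit is 0 or close to it.

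The size of the effect in this trial is unknown, because the documents do not say how many laboratories report in percent. Results collected as absolute counts with absolute ranges are unaffected. The exposure is limited to the descriptive low/normal/high, abnormality and shift displays. Neither the primary efficacy test nor the haemolysis definition uses differentials. This is a modest point, but worth correcting because a stated rule misleads when followed.

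**What to change.** Add to SAP 4.7.3.1 that low/normal/high flags, abnormality counts and shifts for differentials are derived from the result and the local range in the same unit. This can be the original percent against the local percent range, or the converted count against limits that have also been converted. State in the same place that converted counts, calculated as WBC × percent / 100, are used only for quantitative summaries and changes from baseline.

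The cost is about one sentence in the SAP and a matching line in the programming specification. No new data are needed, and no other analysis changes.

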8.2.2. Visit 2: First study drug course

(As soon as the biologic results of screening are available, no later than 4 weeks after the start of the screening).

The following study procedures will be carried out at the 1st study drug course:

- Before the 1st study drug course (within 24 hours before study drug course)
 - Complete physical examination.
 - Biometric information: weight.
 - Vital signs: temperature, heart rate, systolic and diastolic blood pressure.
 - Baseline neurological status assessment:
 - INCAT disability score (adjusted INCAT disability score will be deduced from reported values).
 - Patient and Investigator CGI-S.
 - MRC-sum-score.
 - Rasch-modified MRC sum score.
 - R-ODS.
 - Grip strength with Martin vigorimeter in both hands.
 - Biological tests in local laboratory:
 - Serum total IgG trough levels.
 - C3 and C4 antigens.
 - Serum reference sample for long term storage.
 - Analysis at centralised laboratory:
 - BAFF.
 - CH50.
 - FcγRIIB.

- AEs assessment.
- Listing of concomitant medication.
- Patient diary verification. If information on the patient's diary is not clear, the Investigator will ask the patient questions. The investigator may annotate the patient's diary but must date and sign the annotations.
- During the course of study drug infusion:
 - Collection of infusion parameters.
 - Vital signs measured 30-45 min and 60-75 min after the beginning of the infusion: temperature, heart rate, systolic and diastolic blood pressure.
 - Listing of concomitant medication if applicable.
 - AEs assessment.
- 30-45 min after the end of study drug infusion:
 - Vital signs: temperature, heart rate, systolic and diastolic blood pressure.
 - AEs assessment.
 - Listing of concomitant medication if applicable.

8.2.3. Visit 3: 96 hours after the end of the first course (+/- 24 hours)

The following study procedures will be carried out:

- Complete physical examination.
- Vital signs: temperature, heart rate, systolic and diastolic blood pressure.
- Biological tests in local laboratory:
 - Haematology:
 - Complete blood count + differentials, Hb, MCV, platelets count.
 - Haptoglobin.
 - Biochemical:
 - Creatininemia, glomerular filtration rate according to MDRD.
 - LDH.
 - Total and free bilirubin (total and free bilirubin (total bilirubin in all patients; if total bilirubin > ULN, free bilirubin will be assessed from the same blood sample, as total bilirubin).
 - C3 and C4 antigens.

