To minimize the risk of thromboembolic events, patients with a history of venous thromboembolic disease, myocardial infarction or cerebrovascular accident will be excluded. As well, patients with uncontrolled cardiac arrhythmia and patients with unstable ischemic heart disease will not be allowed to participate to the study.

Acute renal failure

Cases of acute renal failure have been reported in patients receiving IVIg therapy. In most cases, risk factors have been identified. These included pre-existing renal insufficiency, diabetes mellitus, hypovolaemia, overweight, concomitant nephrotoxic medicinal products and age over 65.

To minimize the risk of acute renal failure, patients with a chronic kidney disease (CKD) defined as abnormalities of kidney structure or function, present for >3 months, with implications for health, i.e. patients with persistent albuminuria category A3 and/or GFR <60 mL/min/1.73m² (measured according to the MDRD calculation) will be excluded [39].

The use of loop diuretics is also not allowed if used within 24 hours prior to study drug administration.

Aseptic meningitis syndrome (AMS)

Aseptic meningitis syndrome has been reported to occur in association with IVIg treatment.

Discontinuation of IVIg treatment has resulted in remission of AMS within several days without sequelae. AMS may occur more frequently in association with high-dose of IVIGs.

Haemolytic anaemia

IVIg products can contain blood group antibodies which may act as haemolysins and induce in vivo coating of red blood cells with immunoglobulin, causing a positive direct antiglobulin reaction (Coombs' test) and, rarely, haemolysis. Haemolytic anaemia can develop subsequent to IVIg therapy due to enhanced red blood cells (RBC) sequestration.

Haptoglobin and LDH levels in patients will be assessed at every visit.

Interference with serological testing

After injection of immunoglobulin the transitory rise of various passively transferred antibodies in the patient's blood may result in misleading positive results in serological testing.

Passive transmission of antibodies to erythrocyte antigens, e.g. A, B, D may interfere with some serological tests for red cell antibodies for example the direct antiglobulin test (DAT), direct Coombs' test.

Interaction with other medicinal products

I10E may impair the efficacy of live attenuated virus vaccines for a period of up to 3 months. In the case of measles, this impairment may persist for up to 1 year.

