10.2. Assessment of Safety

The Investigator will ensure that all the AEs occurring during the study are identified and documented in the eCRF. The identification of AEs may come from various sources:

- The Investigator or nurse may clinically observe an AE in the patient at hospital.
- The patient may spontaneously report an AE to Investigator or Nurse.
- From baseline to EOS, the patient will have to document on a patient diary any AE that occurs outside the hospital. This diary will be verified at each visit by the investigator. The patient will be sensibilised to report carefully day and time of TAAEs.
- At each visit the patient will be given a general prompt, e.g. “Did you experience any illness or unusual sign or symptom since your last visit?” in order to ensure that no AE has been forgotten.
- Vitals signs, including systolic and diastolic blood pressures (mmHg), heart rate (beats/minute), and body temperature (°C) will be measured before each infusion, during infusion (30-45 min and 60-75 min after the infusion start) and 30-45 minutes after the end of infusion and will be recorded in the eCRF. Weight will also be recorded before each study drug course, as it is used to calculate the quantity of study drug to be infused.
- Biological tests will be performed at the screening, before each study drug course, 4 days after the first study drug course and at the end of study assessment. Clinically significant abnormality in physical examination or biological tests performed at the screening as per study protocol will be regarded as a medical history.
- The Investigator or a Study Nurse will call the patient 4 days after each treatment course in order to collect information about the possible occurrence of an AE after the patient has left the hospital. The purpose of this phone call is to ensure that all the temporally associated AEs (TAAEs) are tracked.
- If a TAAE is reported by the patient during the phone call, the Investigator will ask the patient additional information at the next visit. If relevant; the Investigator will report the TAAE in the eCRF.

It is the responsibility of the Investigator to collect all the relevant information regarding identified AEs.

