12.10.3. Laboratory data

Laboratory data will be assessed at screening, before each study drug course, after the 1st study drug course, and at the EOS visit. Shift tables will be produced by study drug courses and baseline. Descriptive statistics will be performed. All abnormalities, clinically significant or not will be listed.

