4.3. Demographic and Baseline Characteristics

Unless otherwise specified, the baseline value is defined as the last available value before the first IMP course.

The following characteristics will be summarized in patients of the TTS. If the FAS significantly differs (at least 10%) from the TTS, the characteristics will also be summarized in the FAS.

- Demographic characteristics:
 - Age at screening (years)
 - Age in class: [<65 years and ≥ 65 years]
 - Gender
 - Race
- Clinical examination:
 - Weight (kg)
 - Height (cm)
 - Body mass index (BMI) [kg/m^2] ([section 5.7.1](#))
 - BMI in class: [$<30 \text{ kg}/\text{m}^2$ and $\geq 30 \text{ kg}/\text{m}^2$]
- History of CIDP disease:
 - Time since the date of first symptoms (years) ([section 5.7.1](#))
 - Time since the date of diagnosis (years) ([section 5.7.1](#))
 - Time between first symptoms and diagnosis (years) ([section 5.7.1](#))
 - Diagnostic categories of CIDP
 - * Clinical criteria of CIDP (typical / atypical)
 - * Electrophysiological criteria of definite CIDP
 - * Supportive criteria of CIDP
 - Current INCAT disability score (arms, legs and global non-adjusted INCAT scores and global adjusted INCAT score)
- Prior medications
 - Prior medications will be presented by therapeutic subgroup (level 2) and chemical subgroup (level 4) according to version WHO_DDE_B2_DECEMBER_1_2014 of the World Health Organization's (WHO) Anatomical Therapeutic Chemical (ATC) classification system. The term 'prior medication' refers to any medication given up to 2 months before screening or judged relevant by the Investigator.
- Medical and surgical history
 - Medical and surgical history will be classified by preferred term (PT) and system organ class (SOC) using the version 17.1 of the Medical Dictionary for Regulatory Activities (MedDRA).

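### Visit 2 has no scheduled safety blood panel, so one screening value is both the pre-first-course value and the haemolysis comparator for all eight courses

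*SAP*

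**What the plan says.** SAP 4.7.3.1.2 (Course and infusion level analyses) asks for laboratory summaries "at screening, before and 96h after the 1st IMP course", then before each later course and at EOS. It adds: "The change from before first IMP course to 96h after the 1st IMP course as well as to before subsequent courses will be presented". Screening and the time just before course 1 are thus treated as two different points.

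The same section defines a haemolysis analysis that is evaluated, and reported as a percentage, by course. The mandatory element is "Drop in hemoglobin by at least 1 g/dL compared to baseline". In addition there must be either a positive direct Coombs test or, if that test is not negative, at least two of four markers. Reticulocytes, LDH and bilirubin are compared with baseline; haptoglobin is compared with the lower limit of normal. The section gives no baseline of its own, so the default in SAP 4.3 applies: "Unless otherwise specified, the baseline value is defined as the last available value before the first IMP course".

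Three protocol statements describe when safety bloods are taken:
- 9.2.1: "Haptoglobin and LDH levels in patients will be assessed at every visit".
- 10.2: "Biological tests will be performed at the screening, before each study drug course, 4 days after the first study drug course".
- 12.10.3: "Laboratory data will be assessed at screening, before each study drug course, after the 1st study drug course, and at the EOS visit".

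The visit list in protocol 8.2.2 gives a different picture. Before the first course the local laboratory receives samples only for total IgG, C3/C4 and a stored reference serum. The study plan tables in both documents agree with that list: the blood count, haptoglobin and LDH row and the creatinine, GFR and bilirubin row are marked at Visit 1, blank at Visit 2, and marked again from Visit 3. Visit 2 itself takes place "As soon as the biologic results of screening are available, no later than 4 weeks after the start of the screening".

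**The concern.** Haemolytic anaemia and acute renal failure are among the important potential risks in protocol 9.2.1, and course 1 is the largest dose. Two things follow from the schedule.

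First, for these analytes a column headed before the first course has no scheduled data of its own. A change seen at Visit 3 is measured from screening, so it mixes the effect of the course with any drift during the screening period.

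Second, and more important, the haemolysis analysis is presented by course but tied to one value taken before any treatment. A percentage of courses with haemolysis invites the reader to take it as the chance that a course is followed by haemolysis. With a fixed comparator it does not measure that.

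**Working it through.** **The plan's own figure.** The stated study duration is 24 to 29 weeks (protocol 3.1.5). Screening of 0 to 4 weeks + 21 weeks of treatment + 3 weeks of follow-up = 24 to 28 weeks; the 7-day window makes 29. With the 15-day screening limit of the earlier version (SAP 2.4), 15/7 + 24 = 26.1 weeks, or 27.1 with the window, which fits the SAP's 24 to 27. The windows used below are therefore the plan's own.

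**Age of the comparator at Visit 3.** Inputs: a screening sample up to 28 days before first dose (protocol 3.1.1); a first course of 2 to 5 days, so its last day is at most 4 days after its first (3.1.4); Visit 3 at 96 ± 24 hours after the end of the course, so at most 5 days later (8.2.3); pre-dose assessments within 24 hours before the course (8.2.2).
- Screening value, current version: 28 + 4 + 5 = 37 days at most.
- Screening value, earlier version: 15 + 4 + 5 = 24 days at most.
- Visit 2 pre-dose sample, had there been one: 1 + 4 + 5 = 10 days at most.

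**Age of the comparator at later courses.** The SAP does not say which sample judges a course. I take the next scheduled pre-course sample, nominally at week 3k for course k, with the window anchored at first dose. The maximum age is then 4 + 3k weeks, plus 1 for the window.
- Course 1 judged at Visit 4: 4 + 3 = 7 weeks (8 with the window).
- Course 8 judged at EOS: 4 + 24 = 28 weeks (29 with the window). Under the 15-day limit: 26.1 (27.1).
- The last value before the same course would be about 2 to 4 weeks old, since courses are 3 weeks ± 7 days apart (SAP 4.5.1).

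**What the fixed comparator does to the haemoglobin criterion.** Let b be the screening value, p the last value before a course and c the value after it, in g/dL. The SAP condition is b − c ≥ 1. A per-course condition would be p − c ≥ 1.
- If p = b − d, a further fall of only 1 − d meets the SAP condition. Once d ≥ 1, no further fall is needed, and the haemoglobin condition stays met at each later course until the value recovers.
- If p = b + d, a fall during the course must reach 1 + d before it counts. A new fall of at least 1 but less than 1 + d is missed.

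The LDH, reticulocyte and bilirubin increases behave in the same way.

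**Extreme illustration of recounting.** With 42 patients and 8 courses the denominator is at most 42 × 8 = 336. If one patient met the full criteria after course 1 and they stayed met throughout, that patient would supply 8/336 = 2.4% of courses, against 1/336 = 0.3% if counted once. This shows what the definition permits; it is not a forecast.

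**The case against.** A reader might infer that no blood count is taken before the first dose, or that the change from before course 1 cannot be computed. The documents do not support either. The full panel is drawn at Visit 1, the investigator must check it within 4 weeks before first dose, and both the SAP rule and protocol 3.1.2 make that sample a valid pre-first-course value. What is missing is a separate, more recent one.

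Nor do all three protocol statements conflict equally with the schedule. Visit 2 does include some local tests, so the general wording of 10.2 and 12.10.3 could be read as satisfied. Only 9.2.1 names analytes that are not scheduled there. The conflict could also be settled by correcting the prose. SAP 4.10.2 does this for a similar statement on vital signs, but is silent on laboratory tests.

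The 37 days needs every window at its limit, whereas Visit 2 is meant to follow as soon as the screening results arrive.

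On haemolysis, a fixed pre-treatment baseline is a legitimate choice. It detects a slow cumulative fall that a per-course comparator would miss. A haemoglobin fall alone is not enough, and haptoglobin and Coombs are not compared with baseline. Criteria met again after a new dose may be continuing haemolysis. All of this stands, and it is why the fixed comparison should stay. It does not make the course percentage an incidence, because the haemoglobin drop is required in every case and is always taken from baseline.

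The planned haemolysis listing would show persistence in patients who meet the criteria. It would not bring out falls that the definition misses; those appear only in the general data listings.

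**Conclusion.** The point holds. For blood count, haptoglobin, LDH, bilirubin and creatinine/GFR, the pre-first-course value is the screening value: up to 4 weeks old at first dose under the current version, 15 days under the earlier one. At the extreme it is about 37 days old at Visit 3, where a pre-dose sample would be about 10. The same value is the comparator for the baseline-relative haemolysis criteria at all eight courses, at most about 28 to 29 weeks old for course 8. The percentage of courses with haemolysis is therefore not a per-course incidence.

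A reader might infer that the percentage is biased upwards. The documents do not show that: recounting raises it, missed falls lower it, and the net direction depends on data not given here.

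The conclusion assumes that sites follow the visit list and tables, that the SAP 4.3 default governs because 4.7.3.1.2 does not override it, and that each course is judged on the next scheduled sample. The analysis is descriptive, and the primary endpoint is not affected. The comparator is the more consequential half of the point; the empty time point is mainly a matter of consistency.

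**What to change.** 1. In SAP 4.7.3.1.2, for courses 2 to 8 also evaluate the haemoglobin, LDH, reticulocyte and bilirubin criteria against the last value before that course. Count a course as a new case only if the criteria were not already met before it. Keep the fixed-baseline comparison as a patient-level, cumulative result. Pre-course blood count, LDH, haptoglobin and bilirubin are already collected from Visit 4 on. Reticulocytes are routine only at screening and EOS, so the text should say which value is used when there is no pre-course one, and also which sample judges each course. Cost: a little more analysis and programming, no new data.

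2. State in the SAP that the pre-first-course value for these analytes is the screening value where no Visit 2 value exists, and merge the empty time point with screening. Record this in SAP 4.10.2 beside the vital-signs correction. Cost: a few sentences.

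3. Reconcile protocol 9.2.1, 10.2 and 12.10.3 with 8.2.2 and the study plan tables. If patients are still to be enrolled, add the panel to the pre-dose blood draw already taken at Visit 2; this needs extra local tests but no extra visit. That may no longer be possible: last patient out was planned for Q4 2017, and the SAP cites procedures in force from early 2018. Items 1 and 2 do not depend on it.
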